Figure-18 Box-Plot Chart showing Hb Concentration 48 hours Postpartum in Included Women .

Figure-19 Box-Plot Chart showing Platelet Count 48 hours

Postpartum in Included Women .

Figure-20 Box-Plot Chart showing Liver Transaminases 48 hours Postpartum in Included Women .

Association between the Quantitative Assessment of Schistocytes in Peripheral Blood Smear and Prognosis of Patient Initially Diagnosed as HELLP Syndrome (Study results)

[figure not shown]
[figure not shown]

Figure-21 Box-Plot Chart showing Serum Bilirubin and

Creatinine 48 hours Postpartum in Included Women .

Of the included 100 women, 25 (25%) women showed clinical and laboratory deterioration 48 hours postpartum. All women who deteriorated postpartum received plasma exchange. Of the included 100 women, 3 (3%) died (table-7, figures 22-23).

Table-7 Postpartum Deterioration and Mortality in Included Women .

Postpartum Deterioration	
Yes	25 (25%)
No	75 (75%)
Received Plasma Exchange-steroids	
Yes	25 (25%)
No	75 (75%)
Maternal Mortality	
Yes	3 (3%)

No	97 (100%)
----	-----------

Data presented as number (percentage)

Figure-22 Pie-Chart showing Postpartum Deterioration in Included Women .

[figure not shown]
[figure not shown]

Figure-23 Pie-Chart showing Maternal Mortality in Included Wome .

There were no significant differences between women who deteriorated postpartum and women who did not regarding age, parity or gestational age (table-8, figures 24-26).

Table-8 Difference between Women who Deteriorated Postpartum and Women who did not regarding Initial Characteristics .

	Women who Deteriorated Postpartum (n=25)	Women who Did not Deteriorate Postpartum (n=75)	P
Age (years)			
Range	18 – 35	18 – 38	0.621*
Mean \pm SD	27.08 \pm 4.58	27.65 \pm 5.13	NS
Parity			
Range	1 – 4	0 – 5	0.972**
Median (IQR)	1 (1 – 2)	1 (1 – 2)	NS
Gestational Age (weeks)			
Range	27 – 38	27 – 38	0.407*
Mean \pm SD	33.88 \pm 3.14	34.44 \pm 2.83	NS

SD standard deviation

IQR interquartile range [central 50% of ascendingly-ordered set of data]

[figure not shown]
Data presented as range, mean \pm SD; or range, median (IQR)

* Analysis using Independent Student's t-test

** Analysis using Mann-Whitney's U-Test

NS non-significant

Figure-24 Box-Plot Chart showing Difference between Women who Deteriorated Postpartum and Women who did

not regarding Maternal Age .

Figure-25 Box-Plot Chart showing Difference between Women who Deteriorated Postpartum and Women who did not regarding Parity .

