Table-11 Difference between Women who Died and Women who Survived regarding Schistocytes Percentage .

	Women who Died (n=3)	Women who Survived (n=97)	P
Schistocytes (%) Range	8.3 – 44	0 – 39	<0.001*
Median (IQR)	39 (8.3 – 44)	0.5 (0.1 – 1.1)	HS

[figure not shown]
IQR interquartile range [central 50% of ascendingly-ordered set of data]

Data presented as range, median (IQR)

* Analysis using Mann-Whitney's U-Test

[figure not shown]
HS highly significant

Figure-36 Box-Plot Chart showing Difference between Women who Died and Women who Survived regarding Schistocytes Percentage .

Receiver operator characteristic (ROC) curve was constructed for schistocytes percentage as a predictor of postpartum deterioration in included women. The curve showed a significant predictability as denoted by the significantly large area under the curve (AUC) (figure-37).

Figure-37 ROC Curve for Schistocytes Percentage as Predictor of Postpartum Deterioration in Included Women .

AUC = 0.883, 95% CI (0.770 to 0.996), $p < 0.001$

Table-15 shows the validity of schistocytes at different cutoff values as predictor of postpartum deterioration.

Table-12 Validity of Schistocytes as Predictor of Postpartum Deterioration in Included Women .

Schistocytes	Sensitivity	Specificity	PPV	NPV	FP	FN	LR+
$\geq 0.95\%$	88%	85.3%	66.7 %	95.5 %	14.7 %	12 %	6
$\geq 1.4\%$	84%	96%	87.5 %	94.7 %	4%	16 %	21
$\geq 1.9\%$	80%	98.7%	95.2 %	93.7 %	1.3%	20 %	60

[figure not shown]
PPV positive predictive value -NPV negative predictive value

FP false positive -FN false negative-LR+ positive likelihood ratio

ROC curves were constructed for initial clinical and laboratory data as predictors of postpartum deterioration. Among all measured variables, only initial ALT, initial AST and initial total bilirubin were significant predictors of postpartum deterioration. Their AUCs, though being significantly large, were smaller than the AUC for

schistocytes; indicating that the latter is a more significant and better predictor for postpartum deterioration (figure-38).

Figure-38 ROC Curves for Initial Clinical and Laboratory Data as Predictors of Postpartum Deterioration in Included Women .

Initial SBP: AUC = 0.441, 95% CI (0.324 to 0.559), p=0.381

Initial DBP: AUC = 0.404, 95% CI (0.283 to 0.525), p=0.152

Initial Hb Concentration: AUC = 0.479, 95% CI (0.341 to 0.616), p=0.750

Initial Platelet Count: AUC = 0.429, 95% CI (0.293 to 0.564), p=0.286

Initial ALT: AUC = 0.636, 95% CI (0.484 to 0.787), p=0.043

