Initial AST: AUC = 0.694, 95% CI (0.553 to 0.834), p=0.004

Initial Serum Total Bilirubin: AUC = 0.772, 95% CI (0.656 to 0.887), p=<0.001

Initial Serum Creatinine: AUC = 0.607, 95% CI (0.468 to 0.746), p=0.110

Table-13 shows the validity of initial values of ALT, AST, and total bilirubin as predictors of postpartum deterioration. Again, the validity parameters were remarkably lower than the corresponding parameters of schistocytes.

Table-13 The validity of initial values of ALT, AST, and total bilirubin as predictors of postpartum deterioration.

	Sensitivity	Specificity	PPV	NPV	FP	FN	LR⁺
Initial ALT ≥ 230 u/L	60%	72%	41.7 %	84.4 %	28%	40%	2.1
Initial AST ≥ 240 u/L	60%	84%	55.6 %	86.3 %	16%	40%	3.8
Initial Total Bilirubin ≥ 2.95 mg/dl	68%	81.3%	54.8 %	88.4 %	18.7 %	32%	3.6

ALT alanine transaminase - AST aspartate transaminase

PPV positive predictive value -NPV negative predictive value

[figure not shown]
FP false positive -FN false negative

LR+ positive likelihood ratio

ROC curve was constructed for schistocytes percentage as a predictor of maternal mortality in included women. The curve showed a significant predictability as denoted by the significantly large area under the curve (AUC) (figure-39).

Figure-39 ROC Curve for Schistocytes Percentage as Predictor of Maternal Mortality in Included Women .

Association between the Quantitative Assessment of Schistocytes in Peripheral Blood Smear and Prognosis of Patient Initially Diagnosed as HELLP Syndrome (Study results)

$AUC = 0.985, 95\% CI (0.956 \text{ to } 1.103), p=0.004$

Table-14 shows the validity of schistocytes as predictor of maternal mortality in included women.

Table-14 Validity of Schistocytes as Predictor of Maternal Mortality in Included Women .

Schistocytes	Sensitivity	Specificity	PPV	NPV	FP	FN	LR+
≥ 8.2%	100%	95.9%	42.9%	100%	4.1%	0%	24.3

PPV positive predictive value

NPV negative predictive value

FP false positive

FN false negative

LR+ positive likelihood ratio

There were significant positive correlations between schistocytes percentage and each of systolic and diastolic blood pressures, serum ALT, serum AST, serum total bilirubin and serum creatinine 48 hours postpartum. There were significant negative correlations between schistocytes and each of hemoglobin concentration and platelet count 48 hours postpartum (table-15, figures 40-43).

Table-15 Correlation between Schistocytes and Both Clinical and Laboratory Data 48 hours Postpartum in Included Women .

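### The 95% interval for the mortality AUC ends at 1.103, which is impossible; correcting the digits still leaves a limit above 1, and the Table-14 accuracy figures, based on 3 deaths, carry no intervals

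*SAP*

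**What the plan says.** The SAP's Results chapter reports 3 deaths among 100 women: "Of the included 100 women, 3 (3%) died" (text above Table-7). Table-11 compares schistocyte percentage between "Women who Died (n=3") and "Women who Survived (n=97"). The deaths range from 8.3 to 44 with median 39; the survivors range from 0 to 39.

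Under Figure-39 the ROC result for mortality is "AUC = 0.985, 95\% CI (0.956 \text{ to } 1.103), p=0.004". Table-14 follows, with one cut-off, 8.2% or more: sensitivity 100%, specificity 95.9%, PPV 42.9%, NPV 100% and LR+ 24.3. None of these has an interval. The chapter names no method for the AUC interval, does not mention truncation at 1, and gives no caution about the number of deaths.

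The other AUCs are reported in the same form, for example "AUC = 0.883, 95% CI (0.770 to 0.996") for deterioration under Figure-37 and "Initial Serum Total Bilirubin: AUC = 0.772, 95% CI (0.656 to 0.887") under Figure-38.

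**The concern.** An AUC is the proportion of death-survivor pairs that the marker ranks correctly, so it lies between 0 and 1. A confidence limit of 1.103 cannot be a statement about an AUC. Nor is it a harmless overshoot of the symmetric method used elsewhere, because the upper arm is about four times the lower one.

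Two things are at stake. The stated precision of the mortality AUC cannot be used. In addition, the 8.2% cut-off in Table-14 sits 0.1 point below the lowest fatal value (8.3%). Any cut-off placed there gives 100% sensitivity and 100% NPV in these data, whatever the true accuracy. Without intervals, a reader cannot see how little 3 deaths say about sensitivity.

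**Working it through.** **1. Symmetry of the printed intervals** (Figures 37, 38 and 39; lower arm / upper arm)

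| Predictor | AUC | 95% CI | Arms |
|---|---|---|---|
| Schistocytes, deterioration | 0.883 | 0.770–0.996 | 0.113 / 0.113 |
| SBP | 0.441 | 0.324–0.559 | 0.117 / 0.118 |
| DBP | 0.404 | 0.283–0.525 | 0.121 / 0.121 |
| Hb | 0.479 | 0.341–0.616 | 0.138 / 0.137 |
| Platelets | 0.429 | 0.293–0.564 | 0.136 / 0.135 |
| ALT | 0.636 | 0.484–0.787 | 0.152 / 0.151 |
| AST | 0.694 | 0.553–0.834 | 0.141 / 0.140 |
| Bilirubin | 0.772 | 0.656–0.887 | 0.116 / 0.115 |
| Creatinine | 0.607 | 0.468–0.746 | 0.139 / 0.139 |
| **Schistocytes, mortality** | 0.985 | 0.956–1.103 | **0.029 / 0.118** |

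Mirroring the mortality lower limit gives 2 × 0.985 − 0.956 = 1.014 (1.0125 to 1.0155 allowing for rounding). Mirroring the upper limit gives 2 × 0.985 − 1.103 = 0.867, not 0.956.

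**2. Rebuilding the relevant values**

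- Deaths: n = 3, range 8.3 to 44 and median 39 (Table-11) fix the values at 8.3, 39 and 44.
- Survivors at or above 8.2%: specificity 95.9% = 93/97 and PPV 42.9% = 3/7 (Table-14), so there are 4. The highest is 39 (Table-11).
- Position of the other three: no woman who did not deteriorate exceeds 6 (Table-10), so all 7 values at or above 8.2 belong to the 25 who deteriorated. Table-11 prints the quartiles of three values as 8.3 and 44, which is the (n+1)p rule. For n = 25 the upper quartile is then at rank 0.75 × 26 = 19.5, the mean of the two lowest of those 7. Table-10 gives it as 8.4. Since 8.3 is one of the 7, the lowest must be 8.3 and the next about 8.5, so no survivor lies at 8.2 to 8.3.

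**3. AUC.** The death at 8.3 is ranked above 93 survivors, the death at 39 above 96 with one tie (96.5), and the death at 44 above 97. The sum is 286.5 of 3 × 97 = 291 pairs, so AUC = 0.9845, which rounds to the printed 0.985. The neighbouring totals do not fit: 286/291 = 0.983 and 287/291 = 0.986. A second survivor at 39 is therefore excluded.

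**4. The p-value reproduces.** Null SE = √[(3+97+1)/(12 × 3 × 97)] = 0.170; z = (0.985 − 0.5)/0.170 = 2.85; p = 0.0043.

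**5. Intervals from the rebuilt data**

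| Method | SE | 95% CI |
|---|---|---|
| Hanley-McNeil, nonparametric (ties weighted one third) | 0.0143 | 0.9565 to 1.0126 |
| Same, ties scored one half and squared | 0.0142 | 0.957 to 1.012 |
| DeLong, Wald | 0.0151 | 0.955 to 1.014 |
| DeLong, logit scale | – | 0.901 to 0.998 |
| Stratified percentile bootstrap, 50,000 resamples | – | 0.948 to 1.000 |

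The Wald form is AUC ± 1.96 × SE. For the logit form, log(AUC/(1−AUC)) = 4.154 and its SE = 0.0151/(0.9845 × 0.0155) = 0.993 (unrounded inputs); the limits are then transformed back. The first row has an unrounded lower limit of 0.95650 (just under 0.9565), which rounds to the printed 0.956, and its upper limit rounds to 1.013. No method tried gives 0.956 together with 1.103.

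**6. Exact (Clopper-Pearson) limits for Table-14**

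| Measure | Count | 95% CI |
|---|---|---|
| Sensitivity | 3/3 | 29.2 to 100% (lower limit 0.025^(1/3)) |
| Specificity | 93/97 | 89.8 to 98.9% |
| PPV | 3/7 | 9.9 to 81.6% |
| NPV | 93/93 | 96.1 to 100% (lower limit 0.025^(1/93)) |

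All Table-14 point estimates reproduce from these counts; LR+ = 1/(4/97) = 24.25.

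**The case against.** The Figure-39 line carries typesetting codes that the other AUC lines lack, so the digits 1.103 could have arisen when the PDF was read. That cannot be excluded from the text alone. It does not rescue the interval, because the symmetric upper limit implied by the lower one is still 1.0125 to 1.0155.

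The exact match to 1.013 depends on how ties are weighted; other conventions give 1.012 or 1.014. This is fair, and the digit swap remains an inference. The conclusion needs only that every one of these values exceeds 1.

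The lightest repair would be to truncate at 1 and report 0.956 to 1.000. That removes the impossible value but keeps a lower limit from an approximation that fails this close to 1; the logit-scale lower limit is about 0.90. It is also fair that the two bounded methods differ by about 0.05 at the lower end and that a bootstrap with three event values is weak. The interval should carry that warning.

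Tables 12 and 13 have no intervals either, and the count of 3 deaths is plainly printed. Both are true, but those tables rest on 25 events, not 3. The imprecision in Table-14 falls mainly on sensitivity and PPV; specificity and NPV are reasonably tight.

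The origin of the 8.2% cut-off is not stated. The Protocol names no such value, and the only schistocyte threshold it cites is 1%, so a choice made from these data is the natural reading.

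Finally, the research question concerns deterioration after delivery, in a design labelled a pilot, so mortality is secondary. That limits the consequence but does not make the figure correct.

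**Conclusion.** The concern holds. The upper limit of 1.103 is impossible and inconsistent with the lower limit of 0.956. The symmetric method used elsewhere in the chapter gives about 1.012 to 1.014, so correcting the digits alone does not produce a valid interval. A bounded 95% interval is roughly 0.90 to 0.998 or 0.95 to 1.00, depending on method.

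In Table-14, 100% sensitivity is compatible with a true value as low as 29%, and the PPV of 42.9% with anything from about 10% to 82%.

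The impossibility and the asymmetry rest on the printed figures alone. The recomputed AUC intervals also assume that Tables 10 and 11 use the same quartile rule and that the summary tables are correct. The AUC of 0.985, its lower limit under the symmetric method, p = 0.004, the Table-11 comparison, the Table-14 point estimates and the deterioration AUC of 0.883 (0.770 to 0.996) are not in dispute. This should be fixed, but it does not change the main finding.

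**What to change.** - **Figure-39:** check the digits against the source output, then replace the interval with one that stays within 0 to 1 and name the method. Either logit-DeLong (about 0.90 to 0.998) or stratified percentile bootstrap (about 0.95 to 1.00) will do. Compute it on the raw data, and state that with 3 deaths neither interval is dependable.
- **Table-14 (secondary):** add exact 95% intervals: sensitivity 29.2 to 100%, specificity 89.8 to 98.9%, PPV 9.9 to 81.6%, NPV 96.1 to 100%. Add a footnote that the 8.2% cut-off is exploratory and was derived from the same 3 deaths, unless the authors can show that it was set in advance.
- **Leave unchanged:** the AUC, the p-values and all point estimates.

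The cost is one corrected interval, four added intervals and one footnote, with no new data. The mortality result will look less precise, as it should.
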